## **21.0 Potential Benefits to Subjects**

21.1 *Describe the potential benefits that individual subjects may experience by taking part in the research. Include the probability, magnitude, and duration of the potential benefits. Indicate if there is no direct benefit.*

Response Individuals participating in this research may gain insight through the data collection/assessment process which involves providing thoughtful answers to questions about sexual victimization experiences, the social environment, friendships, and alcohol use. This information will be made available through the dissemination of study findings. In addition, we will post findings on the UB lab websites so that participants may go to that site to read about findings as they come out.

## **22.0 Compensation for Research-Related Injury**

- N/A: The research procedures for this study do not present risk of research related injury (e.g. survey studies, records review studies). This section does not apply.

## **23.0 Economic Burden to Subjects**

23.1 *Describe any costs that subjects may be responsible for because of participation in the research.*

*NOTE: Some examples include transportation or parking.*

Response: There are no costs for which participants in this study are responsible.

## **24.0 Compensation for Participation**

25.1 *Describe the amount and timing of any compensation to subjects, including monetary, course credit, or gift card compensation.*

*Study 1 Remuneration.* Women will be compensated for focus group participation with \$50 in cash. Stakeholders will receive \$25 in cash as a gesture of appreciation.

*Study 2 Remuneration.* Open Trial participants will be paid \$50 in cash for participating in the intervention and feedback sessions. They will receive an additional \$10 bonus if the pair is scheduled for an appointment within 72 hours of being contacted for scheduling.

*Study 3 Remuneration.* Students will receive electronic gift card payments of \$40 for the baseline assessment (which occurs just prior to the intervention) and \$20 for each post-intervention assessment. To encourage participant retention, participants who complete at least 4/6 bi-weekly assessments will receive a \$20 bonus. Stakeholders will receive \$25 in cash as a gesture of appreciation for participation.

## **25.0 Consent Process**

**25.1 Indicate whether you will be obtaining consent.**

**Yes** (*If yes, Provide responses to each question in this Section*)  
 **No** (*If no, Skip to Section 27.0*)

**25.2 Describe where the consent process will take place. Include steps to maximize subjects' privacy.**

Response: For the first study, consent will be obtained in person, when participants come in for their first session. For Study 1 participants, this will be the focus group. For Study 2 &3, participants will consent online when they complete the self-report measures. For these studies, participants will be directed to an online consent form, which provides information about the study. Participants will consent by clicking a button that reads, "I consent". Participants who provide consent will then be directed to a series of questionnaires online Qualtrics.com (see measures table for a complete list).

**25.3 Describe how you will ensure that subjects are provided with a sufficient period of time to consider taking part in the research study.**

Response: All participants will be scheduled for a lab visit. This will occur at least a week in advance, which should give them ample time to consider whether they wish to participate. Further, when participants are consented, they will be informed that there is no pressure to consent, and that if they would like to take time to think it over, they can come in at another date to complete the consent and initial session.

*Describe any process to ensure ongoing consent, defined as a subject's willingness to continue participation for the duration of the research study.*

Response: There is no process for ongoing consent. The participant's participation in the study is voluntary. As such, completion of the online surveys effectively functions as continued and ongoing consent.

**25.4 Indicate whether you will be following "SOP: Informed Consent Process for Research (HRP-090)." If not, or if there are any exceptions or additional details to what is covered in the SOP, describe:**

- *The role of the individuals listed in the application who are involved in the consent process*
- *The time that will be devoted to the consent discussion*
- *Steps that will be taken to minimize the possibility of coercion or undue influence*
- *Steps that will be taken to ensure the subjects' understanding*

Response: We have reviewed the SOP and there will be no substantial deviations from these procedures.

We have reviewed and will be following "SOP: Informed Consent Process for Research (HRP-090)."

**Non-English Speaking Subjects**

**N/A:** This study will not enroll Non-English speaking subjects.  
(*Skip to Section 26.8*)

**Cognitively Impaired Adults**

**N/A:** This study will not enroll cognitively impaired adults.  
(*Skip to Section 26.9*)

### **Adults Unable to Consent**

**N/A:** This study will not enroll adults unable to consent.  
(*Skip to Section 26.13*)

**25.5** *Describe how you will identify a Legally Authorized Representative (LAR). Indicate that you have reviewed the “SOP: Legally Authorized Representatives, Children, and Guardians (HRP-013)” for research in New York State.*

Response: All participants in our study will be over the age of 18. As such, there will be no role for a legally authorized representative.

We have reviewed and will be following “SOP: Legally Authorized Representatives, Children, and Guardians (HRP-013).”

**25.6** *For research conducted outside of New York State, provide information that describes which individuals are authorized under applicable law to consent on behalf of a prospective subject to their participation in the research. One method of obtaining this information is to have a legal counsel or authority review your protocol along with the definition of “legally authorized representative” in “SOP: Legally Authorized Representatives, Children, and Guardians (HRP-013).”*

Response: Though participants may be outside of NY state when they complete online surveys, the research itself is being conducted only in NY state.

**25.7** *Describe the process for assent of the adults:*

- *Indicate whether assent will be obtained from all, some, or none of the subjects. If some, indicate which adults will be required to assent and which will not.*

Response: No assent will be collected. All participants are adults. Consent procedures described above will be used.

- *If assent will not be obtained from some or all subjects, provide an explanation of why not.*

Response: N/A

**25.8** *Describe whether assent of the adult subjects will be documented and the process to document assent.*

Response: N/A. All participants will be able to provide consent.

### **Subjects who are not yet Adults (Infants, Children, and Teenagers)**

**N/A:** This study will not enroll subjects who are not yet adults.  
(*Skip to Section 27.0*)

**25.9** *Describe the criteria that will be used to determine whether a prospective subject has not attained the legal age for consent to treatments or procedures involved in the research under the applicable law of the jurisdiction in which the research will be conducted (e.g., individuals under the age of 18 years). For research conducted in NYS, review “SOP: Legally Authorized Representatives, Children, and Guardians (HRP-013)” to be aware of which individuals in the state meet the definition of “children.”*

Response: All participants will be asked to bring a driver's license or other government issued ID into the session. This is what will be used to confirm that they are over the age of 18.

**25.10 For research conducted outside of New York State, provide information that describes which persons have not attained the legal age for consent to treatments or procedures involved the research, under the applicable law of the jurisdiction in which research will be conducted. One method of obtaining this information is to have a legal counsel or authority review your protocol along the definition of "children" in "SOP: Legally Authorized Representatives, Children, and Guardians (HRP-013)."**

Response: See above. This research is being conducted in the state of NY.

**25.11 Describe whether parental permission will be obtained from:**

**25.12 Describe whether permission will be obtained from individuals other than parents, and if so, who will be allowed to provide permission. Describe your procedure for determining an individual's authority to consent to the child's general medical care.**

Response: N/A

**25.13 Indicate whether assent will be obtained from all, some, or none of the children. If assent will be obtained from some children, indicate which children will be required to assent.**

Response: N/A

**25.14 When assent of children is obtained, describe how it will be documented.**

Response: N/A

## **26.0 Waiver or Alteration of Consent Process**

**N/A:** A waiver or alteration of consent is not being requested.

This project is eligible for the waiver of written documentation of consent because participation presents no more than minimal risk of harm to subjects and involves no procedures for which written documentation of consent is normally required outside of the research context.

## **27.0 Process to Document Consent**

**27.1 Indicate whether you will be following "SOP: Written Documentation of Consent (HRP-091)." If not or if there are any exceptions, describe whether and how consent of the subject will be obtained including whether or not it will be documented in writing.**

 If you will document consent in writing, attach a consent document with your submission. You may use "TEMPLATE CONSENT DOCUMENT (HRP-502)". If you will obtain consent, but not document consent in writing, attach the script of the information to be provided orally or in writing (i.e. consent script or Information Sheet).

Response: See attached consent forms. (3 forms, 1 for each study)

We will be following "SOP: Written Documentation of Consent" (HRP-091).

## **28.0 Multi-Site Research (Multisite/Multicenter Only)**

**N/A:** This study is not an investigator-initiated multi-site study. Does not apply.

## **29.0 Banking Data or Specimens for Future Use**

- N/A:** This study is not banking data or specimens for future use or research outside the scope of the present protocol. This section does not apply.

## **30.0 Drugs or Devices**

- N/A:** This study does not involve drugs or devices. This section does not apply.

## **31.0 Humanitarian Use Devices**

- N/A:** This study does not involve humanitarian use devices. This does not apply.

## Statistical Analysis Plan

*Data preparation.* We will examine patterns of missing data, research dropout rates, therapist adherence and competence, distributional properties of our measures, and correlations among outcome measures. Though we expect some missing data due to attrition, this will be minimal given the short follow-up, the focus on close friend dyads, and employment of rigorous participant retention procedures that have proven effective in our prior work. Importantly, our analytic approach (below) will allow us to include cases with missing data. In the case of one friend dropping out, we will attempt to determine whether the intervention played any role in study attrition. We will examine for FMI and control group differences on baseline measures and demographics, and if differences emerge, we will include the relevant variables as covariates in analysis.

*Treatment Feasibility and Fidelity.* Descriptive analyses of adherence data, refusal rates, follow-up rates, and participant evaluations will be used to guide possible changes in the intervention and to provide information on feasibility and acceptability. Decisions about possible intervention changes will be made with consideration of qualitative data (analysis described above) and investigator input. As noted, we will collect data on fidelity to ensure that the FMI was administered according to protocol and consistent with MI spirit.

*Outcome analyses.* The primary goals of Aim 3 are to evaluate whether (1) FMI increases readiness and reduces perceived barriers to intervene, and increases alcohol knowledge and strategies post-intervention and over the follow-up (2) FMI increases the implementation of friend-based assault-protective behaviors (FAPB) in our 3-month follow-up, and (3) changes in readiness and perceived barriers for protective behaviors, and alcohol knowledge and strategies are associated with implementation of FAPDs at 3-month follow-up (potential mechanisms). We will also examine if quality of the dyad relationship changes as a function of the intervention. Increases or decreases in relationship quality as a function of the intervention would suggest either a positive impact on dyadic relationships or iatrogenic effects of the intervention, respectively. Whether increases in implementation of behavioral strategies are associated with reduced rates of sexual victimization will also be examined. Examination of sexual victimization is exploratory, as victimization rates are expected to be relatively low over the short follow-up period (i.e., approx. 30% across 3 months; Parks et al., 2008). In secondary analyses, we will also consider alcohol use as an outcome variable to examine potential intervention effects on drinking. Given the pilot nature of the R34 mechanism and the smaller sample size, we will focus analysis on effect sizes and whether effects are in the proposed direction. Effect size estimates can be unreliable in small pilot studies (Kraemer et al., 2006); thus, we will report effect sizes ranges (95% confidence bands).

A prominent feature of our design is that individuals are nested within dyads, and this necessitates a data analytic approach that can accommodate nested data structures. Hence, our Aim 3 analyses are built around hierarchical linear models (HLMs). First, we will evaluate group differences on variables from our first post-intervention assessment (i.e. perceived barriers, readiness, alcohol knowledge and strategies, and implementation of FAPBs) using a two level model (individuals nested within dyads). Treatment will be dummy coded (FMI vs. waitlist control group) and included as a level two covariate. Second, we will utilize all data from our three month follow-ups and repeat these analyses using a three-level model (6 repeated measures nested within individuals, and individuals nested within dyads). In these models treatment will be included as a level three covariate. We will use  $\beta$  to describe effect sizes (Cohen, 1988; Selya et al., 2012).

Our burst design provides a rich opportunity to examine whether changes in target constructs of interest (e.g., barriers, skills, alcohol knowledge and strategies) are associated with implementation of FAPBs. For these analyses we will combine the post-intervention data from our FMI and WLC groups after the latter has completed the intervention and follow-up assessments. Combining groups will increase our sample size and provide more stable estimates of effect sizes. For these analyses we will include reports of past week protective behavioral strategies just prior to the intervention and weekly aggregates of variables of interest from our three-month follow-up yielding 7 repeated measures nested within individuals and individuals nested within dyads. Time will be included as a level-1 covariate, and we will

examine change in readiness, perceived barriers, alcohol knowledge and strategies, and implementation of FAPBs. Effect sizes characterizing change will be computed in two ways: 1). Computing a difference score using baseline and the first follow-up divided by the standard deviation of the difference score, and 2). A difference score using baseline and the last assessment of the follow-up divided by the standard deviation of the difference score (Gibbons et al., 1993; Morris & DeShon, 2002). Individual level intercepts and slopes will be output from these models and this will allow us to examine correlations between slopes and intercepts. We expect that reductions in perceived barriers (better self-efficacy, fewer interpersonal concerns), and increases in readiness will be positively related to implementation of FAPBs. Our models will also allow us to include individual characteristics (e.g. assault history, drinking history, relationship, responsibility) to examine their association with change in perceived barriers, skill implementation, etc. (e.g., prior history of sexual assault is related to more or less change in variables our intervention is expected to impact).

In exploratory analyses, we will examine whether increases in implementation of FAPB from baseline to follow-up are associated with rates of sexual victimization. For these analyses we collapse our follow-up data into dichotomous variable indicating whether sexual victimization occurred. Using a two-level HLM (individuals nested within dyads), this dichotomous outcome will be regressed on the intercepts and slopes of FAPBs (described above). Steeper increases in FAPBs are expected to be associated with lower likelihood of sexual victimization at follow-up controlling for baseline levels of sexual victimization. Odds ratio will be used to describe the effect size. Data from stakeholder and exit interviews will be analyzed using qualitative data analytic techniques.

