**Stage 3 Procedures:**

*Intervention: FMI Mini-Controlled Trial with Intensive Follow-Up*

In this stage, we will test the finalized FMI (see **Screening, Eligibility, and Recruitment** above). To do this, we will contrast outcomes among those in this trial (N=24 dyads) with 24 pairs of friend dyads (total dyad N=48) who are randomly assigned to a wait list control condition.

The FMI will consist of a single session. Sessions will be offered on many days and times across the week to accommodate variability in student schedules. Each session will begin with a baseline assessment. In this session, women will be provided with the refined intervention protocol and will have the opportunity to role play and practice implementing the skills and strategies. Following the intervention, participants will be encouraged to utilize the skills and strategies presented in the intervention over the next 12 weeks, whenever they are out with their friend in a social context.

Dyad pairs assigned randomly (stratified on drinking levels, sexual assault history, and age) to the wait list control condition will be assessed once at baseline and again 12 weeks post-baseline. Assessment measures (baseline, 12 weeks) will mirror those administered to women in the FMI condition. At the completion of the 12 week “wait list,” participants will be administered the FMI and followed for 12 weeks. Comparison of outcomes across conditions will allow for stronger inferences about the efficacy of the intervention, will allow for examination of measurement reactivity, and will increase our sample size to examine within person change.

*Follow-up Assessments.* We will conduct bi-weekly online post-intervention assessments (with the first assessment to occur within 2 weeks of FMI completion) for 12 weeks. The bi-

weekly structure will optimally capture women's experiences applying strategies from the intervention. Participants will be reminded of follow-up assessments by phone, text, and email prompt. Individual members of the dyad will be interviewed in the unlikely event that the other member is lost to follow up over the brief follow-up period. At the end of the 12 weeks, participants will be contacted for an exit interview.

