#### **Bi-Weekly Follow-Up Assessment**

**Overview:** Bi-weekly, participants will report on any occasion since the last assessment that the participant was out with the target friend in a social setting. For each such occasion, we will collect information about the context of these occasions (i.e., bar, party, out to dinner), whether there was alcohol, who was present, and whether there was an opportunity for intervention.

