#### **Friend-Based Assault Prevention Behavior Skills (FAPB)**

*Peer-Directed Bystander Behaviors for Sexual Assault Prevention (Baseline, bi-weekly).* We will use the 49-item Bystander Behaviors Scale for Friends (Banyard et al., 2014), which includes 4 subscales (1) the identification of sexual assault risk situations, (2) accessing resources, (3) planning ahead for risk situations, and (4) safety behaviors in risk settings. This measure will be adapted to include a broader

range of protective behaviors based on findings at Stage 1, and some of the items that refer to intimate partner violence will need to be reworded to assess sexual violence. Participants will complete this measure with respect to their target friend (i.e., did they do this for their friend) and also for themselves (i.e., did their friend do this for them?).

*Sexual Assault-Related Protective Behaviors (baseline, bi-weekly for all drinking occasions).* A measure developed by Armstrong et al., the Women's Peer-Directed Protective Strategy questionnaire (WPPS) will be used to evaluate assault-specific protective behaviors. This 24 item measure includes items such as, "I try to be aware and monitor where my friends are at all times," and, "I watch out for my friends in an attempt to keep them away from (risk) situations". Participants will complete this measure for their target friend (i.e., did they do this for their friend?) and also for themselves (i.e., did their friend do this for them?). Participants will be asked to rate frequency and how effective they perceived each behavior to be. They also will rate how they felt about it when they or their friend engaged in the behavior or did not engage in the behavior (when there was an opportunity) using a brief checklist of positive and negative feelings (e.g., good, relieved, safe, guilty, angry, scared). This will be based on information from qualitative participant interviews at earlier stages.

We also will assess whether the intervention resulted in unanticipated or adverse consequences, such as placing undue stress on a member of the dyad, or straining the friendship.

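### The two FMI-versus-waitlist models adjust for baseline only if an undefined difference emerges; always adjusting for the matching baseline value is a cheap gain in precision, small at r = 0.3 and material from about r = 0.5

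*Combined protocol and SAP*

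**What the plan says.** The SAP (Outcome analyses) plans two comparisons of FMI with waitlist.

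- A two-level model at the first post-intervention assessment: "Treatment will be dummy coded (FMI vs. waitlist control group) and included as a level two covariate".
- A three-level model on the follow-ups, with "6 repeated measures nested within individuals, and individuals nested within dyads": "In these models treatment will be included as a level three covariate". The six measures are all follow-ups, so baseline is not among them.

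Neither model names another covariate. The route for anything else is in the SAP's Data preparation paragraph, after a comparison of the arms on baseline measures and demographics: "if differences emerge, we will include the relevant variables as covariates in analysis". Protocol section 16.1 (Aim 3) has the same models and the same rule.

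Matching baseline values are planned. Section 10.3 gives baseline and later assessments for FAPB ("Peer-Directed Bystander Behaviors for Sexual Assault Prevention (Baseline, bi-weekly"), readiness, decisional balance, alcohol awareness and relationship quality. Randomisation is "stratified on drinking levels, sexual assault history, and age" (Stage 3 Procedures), and neither model names those factors.

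Baseline is used elsewhere, but not for the arm contrast. The seven-measure change models pool both arms after the waitlist has received the FMI. The exploratory victimisation regression controls for baseline victimisation, but its predictors are FAPB intercepts and slopes, not arm.

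**The concern.** The SAP puts its weight on effect sizes with 95% confidence bands, and section 16.2 says these are to inform future studies. Band width is therefore a large part of the quality of the result.

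A baseline covariate narrows the band to the extent that it predicts the outcome. A rule triggered by imbalance ignores this. It can leave out a strongly prognostic baseline because the arms happen to be alike, and admit a useless one because they happen to differ. Because no criterion is given, two analysts could also follow the same SAP and report different estimates.

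Without adjustment, part of any chance baseline gap passes into the observed effect. On the assumptions used below, a gap of one standard error (0.233 SD) shifts the estimate by r × 0.233, which is 0.07, 0.12 or 0.16 SD at r = 0.3, 0.5 or 0.7.

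**Working it through.** **The plan's own figure.** Section 16.2 says only that 88 women give power for moderate to large effects. It states no alpha, power, intra-dyad correlation (ICC) or band width. Assuming two-sided 5% and 80% power, the detectable difference is (1.960 + 0.842) × √(2(1 + ICC)/44), which is 0.60, 0.68 and 0.73 SD at ICC 0, 0.3 and 0.5. This agrees with the wording but cannot be matched to a number.

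**Inputs.** From the documents: 24 dyads per arm (Stage 3, Aim 3). Assumed: ICC 0.3, and r = 0.3, 0.5 or 0.7. Here r is the correlation between dyad-mean baseline and dyad-mean outcome at the time point analysed.

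**Formulas.** The variance of a dyad mean is (1 + 0.3)/2 = 0.65, in units of the unadjusted outcome SD.

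- Unadjusted half-width: t(46) × √(2 × 0.65/24) = 2.013 × 0.2327 = 0.468.
- Adjusted half-width: t(45) × √[2 × 0.65 × (1 − r²)/24 × (1 + 1/44)].
- Ratio of adjusted to unadjusted: 1.012 × √(1 − r²). It equals 1 at r = √(1 − 1/1.012²), about 0.15.

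At r = 0.5 the ratio is 1.012 × 0.866 = 0.876, or 12% narrower. At r = 0.3 it is 0.965, at r = 0.7 it is 0.723, and at r = 0 it is 1.012.

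**Simulation, with three readings of the undefined rule.** Mean half-widths in SD units, from analysis of dyad means:

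| Analysis | r = 0.3 | r = 0.5 | r = 0.7 |
|---|---|---|---|
| Never adjust | 0.466 | 0.466 | 0.466 |
| Rule as a 5% test | 0.466 | 0.464 | 0.461 |
| Rule as a 20% test | 0.465 | 0.457 | 0.443 |
| Rule as a gap above 0.1 SD | 0.457 | 0.430 | 0.380 |
| Always adjust | 0.449 | 0.408 | 0.336 |

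Under the 5% test, baseline enters in about 5% of trials and almost none of the gain is recovered. Under the 0.1 SD gap it enters in about 67% of trials. At r = 0.5 that recovers (0.466 − 0.430)/(0.466 − 0.408) = 62% of the gain; across the three r values the figure is roughly 55–65%.

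Type I error is about 5% when baseline is always included. Under the 5% test it is 4.7%, 4.5% and 3.7% at the three r values, and under the 20% test 4.5%, 3.9% and 2.8%. The conditional rule is therefore mildly conservative when r is high.

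**Week 12.** If r were to fall to half its value by then, to 0.15, 0.25 or 0.35, the ratio is 1.000, 0.980 or 0.948. The gain is about 0, 2 or 5%.

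**Adding the strata.** The documents do not give the form of the strata, so three binary dyad-level factors are assumed.

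- If neither baseline nor strata are prognostic, the half-width goes from 0.466 to 0.472 with perfect balance, from 0.467 to 0.476 with blocks of four in eight cells, and from 0.466 to 0.489 with no balance.
- With blocks of four and r = 0.5, adding strata that explain 0, 5, 10 or 20% of dyad-mean variance takes the baseline-adjusted half-width from 0.410 to 0.413, 0.408 to 0.397, 0.410 to 0.384, and 0.411 to 0.353.

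**Sensitivity of the baseline-only result (formula above).** With ICC 0.1 the half-width is 0.431 unadjusted and 0.378 adjusted at r = 0.5. With ICC 0.5 it is 0.503 and 0.441. With 22 dyads per arm (88 women) it is 0.491 and 0.430. The percentage gain hardly changes.

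**The case against.** **No validity error.** A reader might infer that treatment-only models make the contrast biased or inflate false positives. They do not: dyads are randomised, so the unadjusted contrast is unbiased on average, and the conditional rule errs, if anything, on the conservative side. For a development project whose stated focus is feasibility, this is a question of efficiency.

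**The loss depends on unstated quantities.** This stands. The documents give neither r nor the ICC. r may be low where follow-up is scored by occasion and baseline is not: "Bi-weekly, participants will report on any occasion since the last assessment that the participant was out with the target friend in a social setting". The rule may also mean a small gap rather than a test, in which case more than half the gain is already recovered.

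**The six-wave model.** Baseline tends to correlate more strongly with an average of six follow-ups than with a single one, so a reader might infer much larger gains for the three-level model. The design text does not support that: dyads in the "wait list control condition will be assessed once at baseline and again 12 weeks post-baseline". Six concurrent control waves are not planned there, and control data for the first post-intervention model are also in doubt. That conflict is a separate point to reconcile, so no six-wave gain is claimed here.

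**The effect-size scale.** The SAP names a beta-type effect size and cites a guide to Cohen's f². On f², which is scaled by residual variance, adjustment widens the interval. At an observed difference of 0.5 SD the width is 0.350 unadjusted and 0.364, 0.404 and 0.495 at r = 0.3, 0.5 and 0.7. This reflects a larger f², not lost information. It does mean that the claim of narrower bands holds only for a mean difference on a fixed scale, and that the fix must set that scale.

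**The strata.** It would be too strong to say that no between-group analysis will contain them: section 10.3 plans an exploratory look at whether assault history affects efficacy, without giving the model. With no balance and non-prognostic strata, the full adjustment also cancels the gain at r = 0.3 (0.467 against 0.467).

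**Conclusion.** The point holds as a cheap improvement, not as an error of validity. Both between-group models name only treatment, and the one route for baseline selects on chance imbalance by an undefined criterion.

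The result rests on 24 dyads per arm, an assumed ICC of 0.3 and an assumed range for r. On the mean-difference scale, the precision forgone relative to always adjusting is small at r = 0.3, material from about r = 0.5, and nil or slightly negative below about r = 0.15. For a week-12 contrast with a faded correlation it may be only a few per cent. How much of it the conditional rule would recover cannot be settled from the text. The argument applies to whichever FMI-versus-waitlist contrast remains once the control assessment schedule is reconciled.

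**What to change.** 1. In every FMI-versus-waitlist model that remains, prespecify as a fixed covariate the baseline value of the same outcome wherever it is collected: readiness, decisional balance, FAPB, alcohol awareness and relationship quality. Add perceived barriers if its instrument is given at baseline; section 10.3 does not identify a separate one.
2. Include the stratification factors in the dyad-level form used to randomise, and write that form down, including how a dyad is classified when its two members differ.
3. For alcohol strategies personalised during the FMI, which have no clear baseline counterpart, use the stratification factors only.
4. Delete the conditional covariate rule in the SAP and in protocol section 16.1. Keep the baseline comparison as description.
5. Report the adjusted mean difference with its 95% band, standardised by an unadjusted SD (baseline or pooled), so that adjustment does not change the effect-size scale.

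The cost is a few sentences and no new data. If neither baseline nor strata turn out to be prognostic, the half-width grows by about 0.005 SD for baseline alone, by 0.006 to 0.009 SD with strata balanced perfectly or by blocks of four, and by at most about 0.02 SD with no balance. Factors with more than two levels would use further degrees of freedom.
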